NCT01053078

Naltrexone and Hypoglycemia in Type 1 Diabetes

Protocol Approval Date: August 17th, 2012

PI: [name]

Hypoglycemia unawareness is a limiting factor in the treatment of type 1 diabetes and is a very difficult problem to reverse. Using positron emission tomography (PET), Dunn et al have recently demonstrated that patients with type 1 diabetes and hypoglycemia unawareness display a brain activation pattern during hypoglycemia that resembles the activation pattern seen following the administration of an addictive substance such as cocaine (1). In this response, the amygdala and hypothalamic regions associated with stress were less activated and the ventral striatum region associated with motivation and the lateral orbitofrontal cortex region associated with reward were not activated as strongly during hypoglycemia in the unaware compared to the aware subjects. These observations raise the question of whether one reason hypoglycemia unawareness is so difficult to reverse is that it is rewarding and not perceived as a stress to the patient, much like the response an addict has to a drug upon which he has grown dependent. If so, therapies applied to the treatment of addictions might provide a novel approach to the treatment of hypoglycemia unawareness in type 1 diabetes. One such therapy could be the orally administered non-addicting opioid antagonist naltrexone that has been shown to be effective in the treatment of many addictions (2-4).

The long-term goal of this project is to test the hypothesis that naltrexone therapy in subjects with type 1 diabetes and hypoglycemia unawareness will:

- reduce the number of hypoglycemic events (defined as number of episodes of hypoglycemia that require the assistance of another to recognize/treat and as minutes during which blood glucose is < 70 mg/dl as measured by continuous glucose monitoring, both over a 7 day period),
- improve recognition of hypoglycemia during experimental conditions, and
- reduce activation in the ventral striatum and lateral orbitofrontal cortex and increase activation in the amygdala and hypothalamus during hypoglycemia.

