Naltrexone, which can be delivered orally, has been shown to be safe and efficacious in the treatment of various addictive disorders such as alcoholism (4), opiate addiction (2) and pathological gambling (3). The drug binds primarily to the μ opioid receptor and is believed to block the binding of beta-endorphins released from the nucleus accumbens and ventral tegmental areas upon exposure to an addicting drug like alcohol. This blockade in turn ultimately affects downstream activation in regions associated with reward and craving (9). Naltrexone is approved by the Food and Drug Administration for treatment of alcoholism at a dose of up to 50 mg a day for an indefinite period of time but has been used in higher doses to treat pathological gambling (10). Efficacy in reducing alcohol cravings increases with treatment periods longer than 60 days, but were reduced by approximately half after 30 days of treatment (4). The drug has a black box warning about hepatotoxicity at doses above 50 mg/day, but in otherwise healthy out-patients, doses up to 200 mg a day were well tolerated and associated with normal liver function tests for more than a year (11).

During hypoglycemia, intravenous administration of the μ opioid receptor antagonist naloxone enhances the epinephrine and cortisol secretory responses during hypoglycemia in both normal controls and in patients with type 1 diabetes (12). More recently, naloxone infusion during an episode of hypoglycemia prevented the development of hypoglycemia associated autonomic failure in normal controls (13). These observations suggest that a μ opioid receptor antagonist might be of benefit in the treatment of hypoglycemia unawareness through a direct effect on cerebral glucose sensing and/or the coordinated counterregulatory response even if it does not prove to have an effect on the activation of centers involved in motivation and reward.

Preliminary Data

Our research group is very experienced in all aspects of the methodology required to complete this project. We have a long track record of successfully recruiting subjects to participate in complicated metabolic studies (14-19). In recent years, our work has focused on subjects with type 1 diabetes (20, 21), many with hypoglycemia unawareness, and we have developed a registry of such subjects interested in participating in future studies. We also are skilled in the performance of clinical trials, having participated in the ACCORD trial since 1999 (22).

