Subjects between the ages 18 and 65 years of age will be recruited for participation from the University of Minnesota Endocrine Clinic and a registry of volunteers maintained by the investigators. Type 1 diabetes will be defined on clinical grounds. To be categorized as experiencing hypoglycemia unawareness, subjects must first report at the time of initial contact an inability to recognize at least some blood glucose values less than 50 mg/dl during the prior 3 months. At the time of the screening visit, subjects must then be defined as having hypoglycemia unawareness on a Cox questionnaire (24). Exclusion criteria will include concomitant use of acetaminophen, aspirin or ibuprofen (all may increase risk of naltrexone induced liver dysfunction), history of drug or alcohol abuse, current diagnosis or history of psychiatric illness, history of liver disease with elevations in ALT/AST, history of renal insufficiency/failure (creatinine >1.5 mg/dL), pregnancy or breastfeeding, history of seizure or cardiac disease (both of which will increase risk of hypoglycemic clamp), history of stroke, head injury, or other chronic CNS disease, and presence of any characteristics that would preclude placement in the magnet (weight > 300 lbs, presence of metallic implants, etc.).

[figure not shown]
Experimental protocol

The screening visit will occur within two weeks of day zero, which will be the day of the first hypoglycemia study. At the screening visit, informed consent will be obtained and a standardized form will be used to insure subjects meet inclusion/exclusion criteria. Baseline labs for creatinine, ALT, AST, hemoglobin A1c, and CPK will be obtained. The subject will be educated in the use of the continuous glucose monitor and sent home with sufficient supplies to collect data for the seven days before the clamp study on day zero. During this period, subjects will also check their blood glucose before each of three meals and at bedtime and record the values as well as note any episodes in which another person was required to recognize and/or treat hypoglycemia. The continuous glucose monitor display will be blinded to the subject so that it does not influence their diabetes management.

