Subjects will be admitted to the research center the afternoon before the hypoglycemic clamp study on day zero. They will be allowed to take their short acting insulin or a bolus via their pump with their evening meal, but their evening dose of long-acting insulin or their pump will be held after 6 PM. Blood glucose values will then be monitored every 1-2 hours and an intravenous infusion of insulin and/or glucose will be provided to maintain blood sugars between 100-150 mg/dl. Subjects will not be given additional food after their evening meal until the end of the hypoglycemic clamp on day zero.

On the morning of the study, subjects will be transferred to the Center for Magnetic Resonance Research. After their arrival, they will be prepared for clamp study by the placement of one intravenous catheter into one vein in each antecubital fossa for the later infusion of glucose, insulin, and potassium. A third intravenous catheter will be placed retrograde into a vein in the distal leg for later blood sampling. Baseline blood samples for glucose, glucagon, catecholamines, cortisol, and

growth hormone will then be collected no sooner than 30 minutes after catheter placement. At time 0 a constant infusion of insulin will be started at 2.0 mU/kg/min and the subject will be placed into the magnet. Plasma glucose be initially maintained at euglycemia (~100 mg/dl) while the baseline scan is done. Plasma glucose will than be reduced to 50 mg/dl and maintained at this level of glycemia for approximately thirty minutes. During the final 15 minutes subjects will be asked to quantitate their symptoms using a standardized method (25). Blood samples will be obtained every five minutes for measurement of plasma glucose concentration on a nearby analox machine and every twenty minutes for later measurement of glucagon, catecholamines, cortisol, and growth hormone.

Study design. CGMS= continuous glucose monitoring; BG=blood glucose; CASL = continuous arterial spin labeling; hypo= hypoglycemic; safety labs = ALT, AST, Cr, CPK

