Cerebral blood flow will measured on a Siemens 3 Tesla magnet when the subject is euglycemic and again during the final 15 minutes of the hypoglycemic period. A T1 mapping technique will be used in which a RARE sequence with etl=8 echoes and an echo spacing of 7 ms with center-out k-space sampling (effective TE = 7 msec) is employed. CBF contrast will be achieved using FAIR (26)with a 12 msec long HS8 inversion pulse to generate a 6.6 Hz inversion bandwidth above a peak B1 of 500 Hz. A T1-image will be calculated at steady state from three acquired images on a pixel by pixel basis, as previously described (27).

Cerebral blood flow maps will be calculated according to:

$$CBF = \frac{\lambda}{T_1} \frac{S_0 - S_T}{S_T + (2\alpha - 1)S_0}$$

where λ (ml/g) denotes the brain-blood partition coefficient of water, T_1 (s) is the longitudinal relaxation time of tissue water, α is the efficiency of arterial spin labeling, and S_0 and S_T are signal intensities of control and arterial spin labeled images, respectively. Differences in whole brain cerebral blood flow measured during hypoglycemia and euglycemia will be determined for each subject. The perfusion images will then be transformed into Talairach space using the anatomic images and differences between individual regions of interest (such as amygdala, ventral striatum, lateral orbitofrontal cortex, and hypothalamus) during hypoglycemia and euglycemia will be determined for each subject. [name] from the Center for Magnetic Resonance Research will be responsible for the collection and processing of the data collected using the 3 T magnet.

At the completion of the clamp study, subjects will be removed from the magnet, the insulin infusion will be discontinued, glucose will be given to achieve euglycemia, and subjects will be fed a meal. Randomization will then be done and subjects will be sent home with their assigned treatment. An

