Investigational New Drug (IND) approval for the use of this medication for this study has already been obtained from the Food and Drug Administration. The investigational pharmacy at the University of Minnesota Medical Center will insure that the naltrexone and placebo tablets are identical in appearance and will maintain the log of the treatment assignment. Only the study pharmacist will have access to this log until the study is completed. The dose of the drug will be titrated up over 10 days (25 mg daily x 5 days, then 50 mg daily x 5 days, then 50 mg BID x 18 days). Subjects will be asked to avoid use of acetaminophen, non-steroidal anti-inflammatory medications and alcohol while taking naltrexone. At 14 ± 1 days, subjects will return to provide blood for measurement of ALT, AST, CPK, and creatinine. Drug will be stopped in subjects who experience an increase that exceeds two times the upper limit of normal for ALT, AST, or CPK or have a rise in their creatinine to 2.0 mg/dl or above in men or 1.5 mg/dl or above in women.

At the 14 day visit, subjects will be reminded to wear the continuous glucose monitor for the seven days before the next hypoglycemic clamp study and will be sent home with sufficient supplies to do so. On the night before the clamp study, they will be readmitted to the research center for preparation as outlined above. Repeat samples for ALT, AST, CPK, and creatinine will also be collected. On the day of the study, subjects will take their final dose of naltrexone/placebo and be transported to the Center for Magnetic Resonance Reserch to repeat the clamp study with measurement of cerebral blood flow described above.

Statistical analysis

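### The trial gives an opioid antagonist, but neither its exclusions nor its avoidance list names opioid medicines

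*Combined protocol and SAP*

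**What the plan says.** The opening section introduces the study drug by class: "One such therapy could be the orally administered non-addicting opioid antagonist naltrexone". Background and significance adds that it acts mainly at the mu "opioid receptor and is believed to block the binding of beta-endorphins".

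Under Research Design and Methods, Subjects, the medicine and substance-use exclusions are "concomitant use of acetaminophen, aspirin or ibuprofen (all may increase risk of naltrexone induced liver dysfunction), history of drug or alcohol abuse". The remaining exclusions concern psychiatric, liver, renal, seizure, cardiac and central nervous system conditions, pregnancy or breastfeeding, and fitness for the magnet.

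Under Experimental protocol, the on-treatment instruction is: "Subjects will be asked to avoid use of acetaminophen, non-steroidal anti-inflammatory medications and alcohol while taking naltrexone".

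The sequence of contacts is also relevant. On screening: "The screening visit will occur within two weeks of day zero", and at that visit "a standardized form will be used to insure subjects meet inclusion/exclusion criteria". Then: "Subjects will be admitted to the research center the afternoon before the hypoglycemic clamp study on day zero". After the first clamp: "Randomization will then be done and subjects will be sent home with their assigned treatment". The next visit described is at 14 ± 1 days, for safety bloods and a reminder about the glucose monitor.

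**The concern.** The protocol already screens for interacting medicines, but for one hazard only: the reason it gives for excluding three analgesics is liver risk. The more direct conflict, between an opioid medicine and a drug that blocks the opioid receptor, has no matching entry.

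The two lists also steer subjects away from common non-opioid pain relief while saying nothing about opioids. A subject who needs an analgesic during the course is therefore told what not to take, without a warning about the class most directly affected by the study drug.

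What is at stake is patient safety. A subject taking a prescribed opioid who is allocated naltrexone would meet receptor blockade at home. Nothing in the described follow-up is designed to detect it.

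**Working it through.** No statistical calculation applies. The check is a comparison of texts, followed by simple day arithmetic.

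**1. Does any operative rule name opioids?**

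| Place | What it names | Opioid medicines named? |
|---|---|---|
| Exclusions (Subjects) | Three analgesics, abuse history, medical and magnet items | No |
| Screening bloods (Experimental protocol) | Creatinine, ALT, AST, HbA1c, CPK | No |
| Avoidance list (Experimental protocol) | Acetaminophen, NSAIDs, alcohol | No |
| Drug-stopping rule (Experimental protocol) | ALT, AST, CPK, creatinine | No |

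The words opioid and opiate occur once in the opening section and four times in the naltrexone text of Background and significance. They occur 0 times from the start of Research Design and Methods to the reference list.

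**2. Do the existing exclusions catch opioid users by another route?**

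- Opioid combined with acetaminophen, aspirin or ibuprofen: yes, through the analgesic exclusion.
- Opioid user with a history of drug or alcohol abuse: yes, through the abuse exclusion.
- Opioid user with another excluded condition: yes, through that condition.
- Prescribed single-agent opioid, no abuse history, no other excluded condition: not caught.

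The avoidance list leaves the same opening for a single-agent opioid started after randomisation.

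**3. When would a conflict be noticed?**

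Inputs from Experimental protocol: screening up to two weeks before day zero; 25 mg daily for 5 days, 50 mg daily for 5 days, then 50 mg twice daily for 18 days; next visit at 14 ± 1 days. I count the visit from day zero. The day of the first dose is not stated, so I take it as day 0 or day 1.

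- Eligibility check to day zero: up to 14 days.
- Course length: 5 + 5 + 18 = 28 days. Top dose: 2 × 50 = 100 mg a day.
- Next visit: 14 − 1 = day 13, to 14 + 1 = day 15.
- First dose to that visit: shortest 13 − 1 = 12 days, longest 15 − 0 = 15 days.
- The twice-daily step starts after 10 dosing days, on day 10 or day 11. Time on it by the visit: shortest 13 − 11 = 2 days, longest 15 − 10 = 5 days.

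The overnight admission before the clamp falls between screening and dispensing. Its description covers insulin, glucose and food, and mentions no review of medicines. The stopping rule depends on laboratory values, so loss of an opioid's effect would not trigger it.

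**The case against.** The case on the other side has four parts.

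- **The list may not be complete.** The exclusions are introduced as what the criteria will include, which need not be exhaustive. The standardized form, the consent pages and the design figure cannot be seen, and an opioid check could be in any of them. This stands as a limit: the finding is about the visible text. Against it, the form is described as applying the criteria, not adding to them.
- **The documents do not establish the harm.** They describe receptor binding and blockade of endorphins. They say nothing about opioid analgesics, and their one remark on opioid users is favourable: naltrexone is safe and effective in opiate addiction. It stands that loss of opioid effect is an inference. The remark about addiction treatment does not address patients taking a prescribed opioid at the same time as the study drug.
- **The group is small.** A subject must pass every other exclusion, be on a single-agent opioid or start one, and be among the 10 allocated naltrexone. The expected number could be close to zero. This stands too, and is why the grading is modest.
- **Part of the remedy is preference.** No listed exclusion is described as being re-checked at day zero, and silence in a paragraph about clamp preparation is weak evidence that medicines are not reviewed. The time spent on the twice-daily dose measures neither the onset nor the size of harm, since blockade could begin with the first 25 mg tablet; the interval from first dose to visit is the more relevant one. Both points are fair. Neither affects the omission from the two lists.

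**Conclusion.** The concern holds as a point about the visible text. The eligibility rules, applied as written, would admit a person on a prescribed single-agent opioid with no abuse history and no other excluding condition. The avoidance list would not warn a subject who starts one later.

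How often this would happen cannot be stated. What can be stated is the exposure: up to two weeks between the eligibility check and day zero, then 12 to 15 days at home between first dose and next described visit, within a 28-day course.

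The conclusion assumes that no opioid check exists in the unseen form, consent pages or figure. The clinical consequence is limited to loss of the opioid's effect, inferred from the mechanism in the protocol. This is an inexpensive safety improvement, not a flaw that undermines the trial.

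**What to change.** 1. Add current or recent use of opioid-containing medicines to the exclusions under Subjects. The sponsor's physicians should set any opioid-free interval; the documents give no basis for a figure.
2. Add opioid-containing medicines to the avoidance list under Experimental protocol.
3. Put one item on the existing screening form, and ask once more at the existing admission before the first clamp, ahead of randomisation and dispensing, since an opioid may be started after screening. A further question at the 14-day visit is optional.

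If the form or the consent pages already carry this check, the change is only to write it into the protocol. Otherwise the cost is a short amendment: one entry in each of two lists, one form item and one question, with no new visit or test. A few otherwise eligible subjects may be screened out.

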Most relevant to this application is our experience performing hypoglycemic clamp studies while brain activation is studied using magnetic resonance techniques. In our laboratory, we have used continuous arterial spin labeling (CASL) to identify brain regions that are activated in response to insulin-induced hypoglycemia in healthy human subjects (23). Five men and five women (age 29 ± 10 yrs, BMI 23.3 ± 2.1 kg/m², mean \pm SD) participated in this study. CASL images were acquired at euglycemia (99 ± 5 mg/dl) and again during hypoglycemia (52 ± 3 mg/dl) using 2D GE-EPI (labeling time=2500 ms, resolution = $2 \times 2 \times 3$ mm, 100 label/control pairs). In whole brain analysis, increases in regional cerebral blood flow, a measure of neuronal activation, were noted during hypoglycemia relative to euglycemia bilaterally in the medial thalamus, anterior cingulate, and posterior cingulate using BrainVoyager software, as has also been demonstrated by Teves et al using PET (TEVES PNAS 2004). These increases coincided with the peak responses in counterregulatory hormones (glucagon = 110 ± 41 pg/ml, epinephrine = 519 ± 273 pg/ml, norepinephrine = 405 ± 124 pg/ml), providing evidence that activation of these brain regions is involved in the counterregulatory response to hypoglycemia. Focused region of interest analysis of specific regions such as the hypothalamus or amygdala was not performed in this study, but will be performed in the proposed project.

Research Design and Methods:

This study will be a randomized double blind placebo controlled trial involving 20 subjects with type 1 diabetes and hypoglycemia unawareness. Since the time necessary for the effect of naltrexone on our outcome variables to washout after a treatment period is unknown, each subject will serve as their own control and differences between the changes in the outcome measures will be evaluated between groups. The study design is depicted in the figure below.

Subjects

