This is a pilot study in which a sample size of 20 (10 subjects to receive placebo and 10 subjects to receive naltrexone) was arbitrarily selected to determine how large a sample size will be necessary to determine if naltrexone has an effect on our outcome measures. Each subject will serve as his/her own control and changes in the outcome variables (number of hypoglycemic events defined as number of episodes of hypoglycemia that require the assistance of another to recognize/treat and as minutes during which blood glucose is < 70 mg/dl as measured by continuous glucose monitoring, both over a 7 day period); symptom scores collected during hypoglycemia' and differences in regional blood flow noted between the euglycemic and hypoglycemic conditions for each study), will be compared between pre-treatment and end of treatment periods using Student's t-test with correction for repeated measures. [name] from the Department of Biostatistics at the University of MInnesota will assist in the statistical analyses.

Anticipated problems/potential solutions

The most significant problem we may encounter is that our treatment outcomes will be unaffected by naltrexone treatment. Originally, we intended to focus on the effect of naltrexone on cerebral blood flow as a measure of regional activation during hypoglycemia, but since we are unaware of data that demonstrate naltrexone alters brain activation patterns in addicts, we have broadened our outcome measures to include more clinically relevant information such as frequency of hypoglycemia and symptom scores during controlled hypoglycemia. We are hopeful that naltrexone will have an effect on at least one of the outcome variables and will use the data collected from this pilot to design a larger study.

4. Sinclair JD. Evidence about the use of naltrexone and for different ways of using it in the treatment of alcoholism. *Alcohol Alcohol* 2001;36(1):2-10.

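### Assisted hypoglycemia over 7 days is a count analyzed only by a t-test; at low event rates its SD can be zero and cannot size a later trial on this outcome

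*Combined protocol and SAP*

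**What the plan says.** The Statistical analysis section measures hypoglycemic events in two ways: the "number of episodes of hypoglycemia that require the assistance of another to recognize/treat" and continuous-monitor minutes below 70 mg/dl, "both over a 7 day period". Both, together with symptom scores and regional blood flow, "will be compared between pre-treatment and end of treatment periods using" one method: "using Student's t-test with correction for repeated measures".

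On size, "a sample size of 20 (10 subjects to receive placebo and 10 subjects to receive naltrexone) was arbitrarily selected", and the stated purpose is "to determine how large a sample size will be necessary to determine if naltrexone has an effect on our outcome measures".

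The contrast is worded in two ways. Research Design and Methods says that "differences between the changes in the outcome measures will be evaluated between groups". The Statistical analysis section speaks of pre-treatment against end of treatment, which can also be read as a paired test within each arm.

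No rate of assisted episodes is given, and no count model, exact method or rule for empty windows. Entry (Subjects section) requires unrecognized low glucose values and a questionnaire result, not a previous assisted episode.

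**The concern.** A t-test takes its standard error from the SD of change. For a count over one week in 10 subjects per arm, that SD may rest on one or two people, or be exactly zero if nobody's count changes. In that case the t statistic is undefined, and an interval built from it would have no width although the data say very little. The plan does not say what happens then.

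In a pilot meant to size the next study, the SD is one of the main products. A zero SD, or one set by a single episode, gives no usable sample size for this outcome.

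**Working it through.** **The plan's own figure.** The total of 20 is called arbitrary and comes with no alpha, power, effect or SD, so there is no calculation to reproduce.

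**Inputs from the plan.** 10 subjects per arm; one 7-day window before treatment and one at its end. Follow-up is 20 × 2 × 7 = 280 person-days, or 280/365.25 = 0.767 person-years.

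**Assumptions.** Rates r of 1, 2, 3, 6 and 12 episodes per person-year, because the documents give none; Poisson counts; two-sided 5% level; a true halving in the naltrexone arm at end of treatment, or no effect, as stated.

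**Chance that nobody changes.** The mean per subject-week is μ = r × 7/365.25. With no effect, one subject's change is zero with probability p₀ = exp(−2μ)·I₀(2μ), where I₀ is the modified Bessel function. With a halving it is p_h = exp(−1.5μ)·I₀(2μ√0.5). The pooled SD is zero, apart from negligible cases, with probability p₀¹⁰ × p_h¹⁰. At r = 3, μ = 0.0575, p₀ = 0.894 and p_h = 0.919, so 0.894¹⁰ × 0.919¹⁰ = 0.14.

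**Within-arm paired reading, no effect.** At least one arm has SD zero with probability 1 − (1 − p₀¹⁰)². At r = 6, p₀ = 0.805 and p₀¹⁰ = 0.114, giving 1 − 0.886² = 0.215 before rounding of p₀¹⁰ (0.216 unrounded; simulation gives about 21%).

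**Coverage** of the pooled t interval (18 df) was found by simulating 40,000 pilots per rate.

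| Rate per person-year | Pooled SD = 0 (halving) | Coverage of 95% t interval (halving) | At least one arm SD = 0 (paired, no effect) |
|---|---|---|---|
| 1 | 51% | 49% | 90% |
| 2 | 27% | 73% | 72% |
| 3 | 14% | 85% | 55% |
| 6 | 2% | 94% | 22% |
| 12 | <0.1% | 95% | 3% |

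With gamma variation in rates between subjects (shape 0.5), coverage at 1, 2, 3 and 6 per year is similar: 47%, 70%, 82% and 93%.

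**Where the undercoverage comes from.** Given a non-zero SD, coverage at 1, 3 and 6 per year is 99.9%, 99.0% and 96.2%. Multiplying by the chance of a non-zero SD returns the table: 0.49 × 0.999 = 0.49; 0.86 × 0.990 = 0.85; 0.98 × 0.962 = 0.94. The shortfall is almost wholly the zero-SD pilots.

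**Sizing when the SD is not zero.** At 6 per year with no effect, the true variance of change is 2μ = 0.23. The estimated variance has a 5th to 95th percentile range of about 0.2 to 2.1 times that value. Sample size for a fixed difference is proportional to the variance, so the projection spreads equally widely.

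**False positives.** With no effect, the t-test rejects about 0.06%, 1.3% and 3.8% of the time at 1, 3 and 6 per year, below the nominal 5%.

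**Exact limits with no events (two-sided 95%).**
- 0 of 10 subjects: 1 − 0.025^(1/10) = 30.8%.
- 0 of 20 subjects, arms pooled: 1 − 0.025^(1/20) = 16.8%.
- No episodes in 280 person-days: −ln(0.025)/0.767 = 3.689/0.767 = 4.8 per person-year.

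**The case against.** Several points on the other side stand.

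- **The rate is unknown.** A reader might infer that the counts will be almost all zero. The documents do not say so. Subjects are selected for unawareness, and help to recognize an episode counts as well as help to treat it; both could raise the rate. By 12 per person-year the pooled SD is almost never zero and coverage is near nominal.
- **The test is not anti-conservative.** A reader might infer that the t-test produces spurious findings. It rejects too rarely, and once any change is seen its interval is conservative or close to nominal.
- **No zero-width interval is planned.** The section names a test. It promises no confidence interval and no rule for sizing from this SD, and a biostatistician is to assist. A 0-to-0 interval reported as proof of no difference is a possibility, not something the plan states.
- **Other outcomes remain.** Monitor minutes, symptom scores and blood flow can still supply an SD.
- **Exact limits do not create information.** With no events the rate lies between 0 and 4.8 per person-year. The lower end implies an unbounded sample size and the upper end the most favourable one. For a 50% reduction on this change score (80% power, two-sided 5%), the need is 2,867 per arm at 2 per year and 1,147 at 5.
- **Fisher's test at end of treatment is not a better test.** It drops the own-baseline comparison and is stricter: 4/10 against 0/10 gives p = 0.087, while the t-test with four subjects changing by one episode gives 0.025.

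What survives is narrower: the plan states no rate that would place it in the safe range, and gives no instruction for sparse or empty windows.

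**Conclusion.** The point holds for one outcome and for low rates. Under Poisson counts and a true halving, the pooled SD is zero in about half of pilots at 1 per person-year, one in seven at 3 and one in fifty at 6. The within-arm paired reading is more exposed. Above about 3 per person-year collapse of the pooled SD is uncommon, though at 6 the variance estimate is still too loose for confident sizing.

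The wider conclusion that the pilot cannot size the next trial is not supported; the limit applies to sizing on assisted episodes. All percentages rest on assumed rates. This is a cheap improvement to analysis and reporting, not a flaw in the trial as a whole.

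**What to change.** Add a short paragraph to the Statistical analysis section for assisted episodes:

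1. Report, for each arm and window, the episodes, person-days and number of subjects with at least one episode, with exact Poisson intervals for the rate and Clopper-Pearson intervals for the proportion.
2. If a between-arm test is wanted, use a permutation test on each subject's change. This keeps the own-baseline comparison, which Fisher's test at end of treatment alone does not.
3. Base any sizing on this outcome on a range of rates within the exact limits, not on the SD of change. If there are no events, say that the pilot cannot size a trial on it.

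This costs a few lines of text and no new data or change in conduct. The intervals will be wider and less favourable, and there is no gain in power.
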